11.4.3 Analyses of safety data

All safety analysis will be performed in two analysis sets for the safety population as defined in [Section 11.4](#). The baseline value for the applicable safety parameters is the original baseline from the parent study.

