2.1.4.4 Vital signs variables

Vital signs include blood pressure (mmHg), heart rate (beats per minute), respiratory rate (breaths per minute), body temperature (degrees Celsius) and body weight (kg) will be measured at every scheduled visit. Height (cm) will be measured at Visit 1 (Week 0) and Visit 10 (Week 52/EOT). Baseline values for vital signs will be the original baseline from the parent study.

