2.4.5 Analyses of safety data

The summary of safety results will be presented for each analysis set ([Section 2](#)) of safety population by the treatment category, unless otherwise specified.

General common rules

All safety analyses will be performed on the safety population as defined in [Section 2.3.1](#), unless otherwise specified, using the following common rules:

- Safety data in patients who do not belong to the safety population (eg, exposed but not enrolled) will be listed separately (if applicable).
- The baseline value for safety parameters is defined as the original baseline from the parent study.

- In addition to the baseline values, the pre-dose measurements at Week 0 in LTS14424 will be presented in the by-visit summary/figure for laboratory, vital signs or ECG parameters. The pre-dose measurements at Week 0 are the last available measurements prior to the first IMP dose in LTS14424 study.
- The potentially clinically significant abnormality (PCSA) values are defined as abnormal values considered medically important by the sponsor according to predefined criteria/thresholds based on literature review and defined by the sponsor for clinical laboratory tests, vital signs, and ECG ([Appendix A](#)).
- PCSA criteria will determine which patients had at least 1 PCSA during the analysis set specific treatment-emergent adverse event period as defined in [Section 2](#), taking into account all evaluations performed during the treatment-emergent adverse event period, including non-scheduled or repeated evaluations. The number of all such patients will be the numerator for the on-treatment PCSA percentage.
- The treatment-emergent PCSA denominator for a given parameter will be based on the number of patients assessed for that given parameter in the treatment-emergent adverse event period for each analysis set of safety population by the treatment category.

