2.4.5.4 Analyses of vital sign variables

The baseline value of all vital sign variables is the original baseline from the parent study. The pre-dose measurement at Week 0 of LTS14424 will be separately presented in the summaries or plots over time.

The summary statistics (including number, mean, median, standard deviation, Q1, Q3, minimum and maximum) of all vital signs variables (measurements and changes from baseline) will be calculated for each visit or study assessment (baseline, each post-baseline time point, and endpoint) for each analysis set ([Section 2](#)) of safety population by the treatment category. For all vital sign variables, the mean change from baseline with corresponding standard error at each visit will be plotted for each analysis set of safety population by the treatment category.

For all vital sign variables, the summary statistics over visits for either measurements or mean change from baseline, and the plot of mean change from baseline over visits should include the measurements obtained at either scheduled or unscheduled visits.

The incidence of PCSAs (list provided in [Appendix A](#)) at any time during the treatment-emergent adverse event period as defined in [Section 2](#) will be summarized for each analysis set of safety population by the treatment category irrespective of the baseline level and/or according to the following status at baseline of parent study and at Week 0 of LTS14424 study, respectively:

- Normal/missing.
- Abnormal according to PCSA criterion or criteria.

For PCSA analyses, the vital sign measurements obtained at either scheduled or unscheduled visits should be used.

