| | 6 to <12 years old (Children) | < 18 per minutes > 30 per minutes | |
| | 12 to 16/18 years old (Adolescents) | < 12 per minutes > 20 per minutes | |
| SaO2 | All age ranges | ≤ 95 % | |
| Weight | All ranges | ≥ 5 % weight loss from baseline | Based on identification of trends in the child's growth with a series of visits WHO Multicentre Reference Study Group, 2006; Center for Disease Control. Growth chart 2007 |

**CRITERIA for POTENTIALLY CLINICALLY SIGNIFICANT ABNORMALITIES
For Studies in Children**

| Parameter | Age range | PCSA | Comments |
|---------------------------|----------------|-------------------------------------------------------------------------------------------------------------|----------------------------------------------------------------------------------------------------------------------------------------------------------------------------------------------------------------------------------------------------------------------------------------------------------------------------------------------|
| Clinical Chemistry | | | Ref Molleston JP et al. JPN 2011; Moritz et al., Pediatrics 1999; Moritz et al., Pediatr Nephrol 2005 ; Sedlacek et al., Seminars in Dialysis 2006) Gong G et al. Clinical Biochemistry 2009; Masilamani et al. Arch Dis Children 2012; Mulberg AE et al. Pediatric Drug Development Concepts and applications. John Wiley & sons, Inc. 2009 |
| ALT/SGPT | All age ranges | ≥ 3 ULN By distribution analysis: ≥ 3 ULN ≥ 5 ULN ≥ 10 ULN ≥ 20 ULN | Based on normal ranges: 6 to 50 U/L (0-5 days), 5 to 45 U/L (1-19 years) |
| AST/SGOT | All age ranges | ≥ 3 ULN By distribution analysis: ≥ 3 ULN ≥ 5 ULN ≥ 10 ULN ≥ 20 ULN | Based on normal ranges: 35 to 140 U/L (0-5 days), 15 to 55 U/L (1-9 years), 5 to 45 U/L (10-19 years) |
| Alkaline Phosphatase | All age ranges | ≥ 1.5 ULN | Based on normal ranges: 145 to 420 U/L (1-9 years), 130 to 560 U/L (10-11 years), 200 to 495 U/L (Boys 12-13 years), 105 to 420 U/L (Girls 12-13 years), 130 to 525 U/L (Boys 14-15 years), 70 to 130 U/L (Girls 14-15 years), 65 to 260 U/L (Boys 16-19 years), 50 to 130 U/L (Girls 16-19 years) |
| Total Bilirubin | All age ranges | ≥ 1.3 ULN | $CF = mg \times 1.7 = \mu mol$ Based on normal ranges: <6 mg/dL (Term 0-1 day), <8 mg/dL (Term 1-2 days), <12 mg/dL (Term 3-5 days), <1 mg/dL (Term >5 days) |

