3 STATISTICAL ANALYSES

3.1 GENERAL CONSIDERATIONS

In general, continuous data will be summarized using the number, mean, standard deviation (SD), median, minimum, and maximum for observed data and the change from baseline. Categorical and ordinal data will be summarized using the count and percentage of participants.

The baseline values for efficacy, safety, PK, ADA and other endpoints are defined as the last available measurements prior to the first IMP dose if the participant is treated, or the last available value up to enrollment if the participant is not exposed to IMP.

Unless otherwise specified, all analyses will be performed on each dose regimen group and overall.

Observation period

The observation period will be divided into 4 segments:

- The **pre-treatment period** is defined as the period up to first IMP administration.
- The **treatment-emergent (TE) period** is defined as the period from the first IMP administration to the last IMP administration + 98 days for participants with IMP on 100 mg/200 mg q2w regimen, or to the last IMP administration + 112 days for participants on 300 mg q4w regimen. The treatment-emergent period includes the following 2 periods:
 - The **on-treatment period** is defined as the period from the first IMP administration to the last administration of the IMP + 14 days for participants with IMP on 100 mg/200 mg q2w regimen, or to the last administration of IMP + 28 days for participants on 300 mg q4w regimen.
 - The **residual treatment period** is defined as the period from the end of the on-treatment period to the end of the treatment-emergent period.
- The **post-treatment period** is defined as the period from the end of the treatment-emergent period.

The on-study observation period is defined as the time from start of intervention until the end of the study defined as the status date collected on e-CRF page “Completion of End of Study”.

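### The main-study weight-loss flag is measured against a parent-study weight one to two years old, so growth since then makes it insensitive to loss during LTS14424

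*SAP*

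**What the plan says.** The weight criterion in main-study SAP Appendix A (vital signs) is "≥ 5 % weight loss from baseline", for all ages.

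The reference is fixed in several places, none of which makes an exception for weight:

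- SAP 2.1.4.4: "Baseline values for vital signs will be the original baseline from the parent study".
- SAP 2.4.5: "The baseline value for safety parameters is defined as the original baseline from the parent study".
- SAP 2.4.5.4: "The baseline value of all vital sign variables is the original baseline from the parent study".
- Protocol 11.4.3: "The baseline value for the applicable safety parameters is the original baseline from the parent study".

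On the counting window, SAP 2.4.5 states: "PCSA criteria will determine which patients had at least 1 PCSA during the analysis set specific treatment-emergent adverse event period". SAP Table 3 ends that period 14 weeks after the last dose on the two-weekly regimens and 16 weeks after it on 300 mg q4w.

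LTS14424 Week 0 has two roles in SAP 2.4.5.4. It is shown separately in by-visit summaries and plots, and PCSA incidence may be split "according to the following status at baseline of parent study and at Week 0 of LTS14424 study, respectively". Neither makes it the reference for the percentage loss.

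The Japan substudy SAP (3.1) differs: its baseline values are "defined as the last available measurements prior to the first IMP dose if the participant is treated".

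**The concern.** Weight rises with age in this population. Patients were 6 to 11 years old at parent baseline, and the plan itself expects gain, since it has a dosing rule for children who cross 30 kg. A loss criterion tied to a fixed early weight loses sensitivity as the child grows.

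Weight is also the most exposed vital sign. In Appendix A the blood pressure criteria pair a change from baseline with an absolute limit, and temperature, respiratory rate and oxygen saturation use absolute limits. Weight alone rests entirely on change from baseline. The appendix comment explains the criterion by growth trends over a series of visits, which a single old value does not capture.

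The weight PCSA is the planned per-patient count of relevant weight loss in a long-term paediatric safety study. In the Placebo-Dupilumab category, Week 0 is the last weight before any dupilumab, so the current flag offsets a loss on drug with a year of growth on placebo. A reassuringly low incidence could not be read as absence of weight loss during LTS14424.

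**Working it through.** The plan states no figure to reproduce; the check is on what the definition implies.

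**Age of the reference.** SAP 1.1 equates LTS14424 Week 0 with parent Week 52.

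- Week 0: 52 weeks.
- Week 52: 52 + 52 = 104 weeks.
- End of the treatment-emergent period: last dose at Week 50 + 14 weeks (q2w), or Week 48 + 16 weeks (q4w). Both give Week 64, so 52 + 64 = 116 weeks.
- Latest COVID-19 entrants (12 weeks after the parent end-of-study visit), assuming a 12-week parent follow-up, which is not stated: Week 0 at 52 + 12 + 12 = 76 weeks, then 128 weeks at Week 52 and 140 at Week 64.

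**Loss needed to trigger the flag.** Let W be parent-baseline weight and r the annual gain. The flag fires at 0.95 × W or below.

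- From Week 0 weight, W(1 + r): 1 − 0.95/(1 + r).
- From the Week 52 weight expected had growth continued: 1 − 0.95/(1 + r)².
- From the expected Week 64 weight: 1 − 0.95/(1 + r)^(116/52).

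With r = 0 all three return 5.0%, the nominal criterion. Growth rates are not in the documents; r = 3% to 15% is an assumed range.

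| r per year | From Week 0 | From expected Week 52 | From expected Week 64 |
|---|---|---|---|
| 3% | 7.8% | 10.5% | 11.1% |
| 5% | 9.5% | 13.8% | 14.8% |
| 10% | 13.6% | 21.5% | 23.2% |
| 15% | 17.4% | 28.2% | 30.4% |

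**Which losses from Week 0 are missed.** A loss of exactly 5% leaves 0.95 × W(1 + r), which exceeds 0.95 × W for any r > 0. A 10% loss is missed when 0.90(1 + r) > 0.95, that is r > 0.95/0.90 − 1 = 5.56%.

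**Example, 30 kg at parent baseline (flag at 28.5 kg or below).**

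- r = 5%: 31.5 kg at Week 0. A 5% loss gives 29.9 kg, not flagged; a 10% loss gives 28.35 kg, flagged.
- r = 10%: 33.0 kg at Week 0. A 10% loss gives 29.7 kg, not flagged.

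**The case against.** The parent baseline is a deliberate and consistent choice, set in protocol 11.4.3 for all safety parameters. It serves the cumulative question and is the only pre-dupilumab reference for Dupilumab-Dupilumab patients. That stands, and is why the existing flag should stay.

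Weight is also covered elsewhere: by-visit summaries with Week 0 shown, worst-value summaries (SAP 2.4.5), flagged listings (protocol 11.4.3.1.4), weighing at every onsite visit, and the instruction in protocol 10.6.3 to watch for weight loss as a sign of infection. These make it less likely that a serious case is overlooked, but none counts patients who lost 5% or more since entering LTS14424. The summaries describe distributions, PCSA flags in the listings inherit the same reference, and protocol 10.4.3 makes a vital-sign abnormality an adverse event only if it meets stated conditions, such as symptoms or a need for treatment. Status at Week 0 is itself judged against the parent baseline.

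The size rests on assumed growth. That is fair: the Week 52 and Week 64 columns compare with a hypothetical growth curve, and their top values need 15% growth compounded over two years or more. The loss from Week 0 is the more direct measure; at 3% to 5% growth it is 7.8% to 9.5%. A very small gain also matters little: it hides a loss of exactly 5% but not one slightly larger.

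Finally, the Week 64 figures do not apply in the modified analysis set to patients who switch to 300 mg q4w, whose window closes the day before the first such dose. This is a minor exception.

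**Conclusion.** The point holds. The main-study weight PCSA uses only the parent-study weight as its reference, and for any child who gained weight in the parent year the effective threshold for loss during LTS14424 exceeds 5%. The direction follows from the definition. The size depends on growth rates absent from the documents: 7.8% to 17.4% of Week 0 weight for assumed gains of 3% to 15% per year, and more against expected weight later in the study.

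The consequence is limited. The table is descriptive, and the primary endpoint and the efficacy analyses do not depend on it. The change is worth making because it is cheap and fills a real gap in the per-patient safety tables.

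**What to change.** In SAP 2.4.5.4 and Appendix A, keep the parent-baseline weight PCSA and report beside it, by treatment category, a second weight PCSA: loss of 5% or more from the LTS14424 Week 0 pre-dose weight. A version against the highest earlier on-study weight is optional; if used, label it as more prone to false flags from measurement noise.

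The data exist: protocol 10.1.1 excludes body weight from the Visit 1 waiver, and weight is recorded at each onsite visit. Protocol 11.4.2 already plans supplemental change from the current-study baseline for selected efficacy variables, so a second reference is not foreign to the plan.

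The cost is one derivation and one table line. There are two downsides. Weight would have two references while other vital signs have one. The new line is also diluted by on-study growth: at Week 52 it needs a loss of 1 − 0.95/(1 + r), or 7.8% to 17.4% of expected weight, against 10.5% to 28.2% for the current flag. It is an improvement, not a full correction for growth.

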Appendix B Summary of statistical analyses

EFFICACY ANALYSIS

| Endpoint | Analysis population | Primary analysis | Statistical Method | Supportive analysis | Subgroup analysis | Other analyses |
|-----------------------------------------------------------------------------------------|---------------------|---------------------------------------------------------------------------------------------|---------------------------------------------------------------|---------------------|-------------------------------------------------------------------------------------------|----------------|
| FEV1, % Predicted FEV1, FVC and FEF 25-75% | Safety | Measurement and change from baseline at all visits | Descriptive statistics based on two sets of safety population | No | Yes (Baseline ICS dose, EOS count, FeNO, type 2 inflammation phenotype and age subgroups) | No |
| Severe exacerbation: number of events/annualized event rate during the treatment period | Safety | Summary of number/annualized rate of severe exacerbation events during the treatment period | Descriptive statistics based on two sets of safety population | No | Yes (Baseline ICS dose, EOS count, FeNO, type 2 inflammation phenotype and age subgroups) | No |

SAFETY ANALYSES

| Endpoint | Analysis population | Primary analysis | Statistical Method | Supportive analysis | Subgroup analysis | Other analyses |
|-------------------------------------------|---------------------|------------------------------------------------------|---------------------------------------------------------------|---------------------|--------------------------------------------------|----------------|
| Adverse events | Safety | Follow safety guidelines | Descriptive statistics based on two sets of safety population | No | Yes (Race, Sex, Ethnicity, and Weight subgroups) | No |
| Lab/vital signs/physical examination/ECGs | Safety | Follow safety guidelines; PCSA analysis; Descriptive | Descriptive statistics based on two sets of safety population | No | No | No |

Appendix C Low, Medium, and High daily doses of Inhaled Corticosteroids (Children 6-11 years) - Estimated clinical comparability

| Inhaled Corticosteroid | Total Daily Dose (mcg) | | |
|----------------------------------|------------------------|-----------|-------|
| | Low | Medium | High |
| Beclometasone dipropionate (CFC) | 100-200 | >200-400 | >400 |
| Beclometasone dipropionate (HFA) | 50-100 | >100-200 | >200 |
| Budesonide (DPI) | 100-200 | >200-400 | >400 |
| Budesonide (HFA) | 100-200 | >200-400 | >400 |
| Budesonide (nebulus) | 250-500 | >500-1000 | >1000 |
| Ciclesonide (HFA) | 80 | >80-160 | >160 |
| Flunisolide (HFA) | 160 | >160-320 | 320 |
| Fluticasone propionate (DPI) | 100-200 | >200-400 | >400 |
| Fluticasone propionate (HFA) | 100-200 | >200-500 | >500 |
| Mometasone furoate | 110-220 | ≥220-440 | ≥440 |
| Triamcinolone acetonide | 400-800 | >800-1200 | >1200 |

CFC = chlorofluorocarbon propellant; DPI = dry powder inhaler; HFA = hydrofluoroalkane propellant; nebulus = nebulized solution

Source: Adapted from Global Initiative for Asthma (GINA) 2018 guidelines with the addition of Budesonide HFA and Flunisolide HFA information; modify low level of Mometasone furoate to 110-220.

Appendix D Definition of Anaphylaxis

"Anaphylaxis is a serious allergic reaction that is rapid in onset and may cause death."

(Adapted from Sampson HA, Munoz-Furlong A, Campbell RL, Adkinson NF, Bock SA, Branum A, et al. Second symposium on the definition and management of anaphylaxis: Summary report—Second National Institute of Allergy and Infectious Disease/Food Allergy and Anaphylaxis Network symposium. *J Allergy Clin Immunol* 2006; 117: 391-397)

Clinical criteria for diagnosing anaphylaxis

Anaphylaxis is highly likely when any one of the following 3 criteria are fulfilled:

1. Acute onset of an illness (minutes to several hours) with involvement of the skin, mucosal tissue, or both (eg, generalized hives, pruritus or flushing, swollen lips-tongue-uvula)
AND AT LEAST ONE OF THE FOLLOWING
 - a. Respiratory compromise (eg, dyspnea, wheeze-bronchospasm, stridor, reduced PEF, hypoxemia)
 - b. Reduced BP or associated symptoms of end-organ dysfunction (eg, hypotonia [collapse], syncope, incontinence)
 2. Two or more of the following that occur rapidly after exposure to a *likely allergen for that patient* (minutes to several hours):
 - a. Involvement of the skin-mucosal tissue (eg, generalized hives, itch-flush, swollen lips-tongue-uvula)
 - b. Respiratory compromise (eg, dyspnea, wheeze-bronchospasm, stridor, reduced PEF, hypoxemia)
 - c. Reduced BP or associated symptoms (eg, hypotonia [collapse], syncope, incontinence)
 - d. Persistent gastrointestinal symptoms (eg, crampy abdominal pain, vomiting)
 3. Reduced BP after exposure to *known allergen for that patient* (minutes to several hours):
 - a. Infants and children: low systolic BP (age specific) or greater than 30% decrease in systolic BP*
 - b. Adults: systolic BP of less than 90 mm Hg or greater than 30% decrease from that person's baseline
-

PEF, Peak expiratory flow; *BP*, blood pressure.

*Low systolic blood pressure for children is defined as less than 70 mm Hg from 1 month to 1 year, less than $(70 \text{ mm Hg} + [2 \times \text{age}])$ from 1 to 10 years, and less than 90 mm Hg from 11 to 17 years.

1 INTRODUCTION

1.1 STUDY DESIGN

The LTS14424 Japan substudy is a multicenter, open-label, single-arm, 1-year treatment study to evaluate the efficacy, safety, and tolerability of dupilumab in Japanese pediatric participants aged 6 to <12 years with uncontrolled, persistent asthma.

For participants with body weight >30 kg, the dose regimen is 200 mg q2w. For participants with body weight \geq 15 kg to \leq 30 kg, they were randomized in a 1:1 allocation ratio to dose regimen of either 100 mg q2w or 300 mg q4w. The dose regimen determined at baseline has been maintained and will not be adjusted upon weight gain or loss during the treatment period.

After a screening phase of 4[\pm 1] weeks, participants were enrolled or randomized in the three dose regimens, and treated open-label for 52 weeks. Upon completion of the treatment period or following early discontinuation of investigational medicinal product (IMP), participants continue into a post-treatment period of 12 weeks. Thirteen participants were enrolled and a minimum of 3 participants were assigned to treatment with each of the 3 dose regimens.

1.2 OBJECTIVES AND ENDPOINTS

Objectives

The primary objective of this substudy is to evaluate the efficacy of dupilumab in children from Japan who are 6 to <12 years of age with uncontrolled, persistent asthma.

The secondary objectives of this substudy are:

- To evaluate the safety and tolerability of dupilumab in Japanese pediatric patients with asthma.
- To evaluate dupilumab in Japanese pediatric patients with asthma with regard to:
 - Systemic exposure,
 - anti-drug antibodies (ADAs),
 - Biomarkers.

Endpoints

The primary endpoint of this substudy is change from baseline in pre-bronchodilator % predicted FEV1 at Week 12.

The secondary endpoints of this substudy include:

- Annualized rate of severe asthma exacerbation events, during the treatment period.
- Change from baseline in pre-bronchodilator % predicted FEV1 at Weeks 2, 4, 8, 24, 52, and 64.

- Change from baseline in other lung function measurements (absolute FEV1, FVC, FEF 25-75%) at Weeks 2, 4, 8, 12, 24, 52, and 64.
- Change from baseline at Week 2, 4, 8, 12, 24, 36, 52, and 64 in ACQ-IA.
- The number (n) and percentage (%) of patients experiencing any treatment-emergent adverse event.
- Serum dupilumab concentrations.
- ADAs.
- Serum: Total immunoglobulin (IgE).
- Fractional exhaled nitric oxide (FeNO).

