Laboratory tests, vital signs, physical examination, or electrocardiogram (ECG) abnormalities are to be recorded as AEs only if they meet the criteria defined in [Section 10.4.3](#), and are assessed as described in [Section 17.7.2.8.3.5](#), [Section 17.7.2.8.3.2](#), [Section 9.1.2](#) and [Section 17.7.2.8.3.4](#). In addition to assessment of primary endpoint, below parameters are used on an ongoing basis during the study to monitor safety of participants and will be presented in a descriptive manner.

17.7.2.8.3.2 Vital signs

Vital signs including blood pressure (mmHg), heart rate (beats per minute), respiratory rate (breaths per minute), and body temperature (degrees Celsius) will be measured at each onsite visit except for IMP administration only visits.

Vital signs will include height (cm) and body weight (kg). Height will be measured at each onsite visit except for the IMP administration only visit and Visit 9 (Week 36). Weight will be measured at each onsite visit except for the IMP administration only visit.

17.7.2.8.3.3 Physical examinations

See [Section 9.1.2](#).

17.7.2.8.3.4 Electrocardiograms

Electrocardiogram (ECG) variables will be recorded by a standard 12-lead ECG. ECGs will be performed at screening, EOT, and EOS (see [Section 17.7.2.2.2](#)).

17.7.2.8.3.5 Clinical laboratory values

Abnormal laboratory values that are considered to be clinically significant by the Investigator should be repeated as soon as possible after receiving the laboratory report to rule out laboratory error. Persistent abnormal laboratory values should be repeated until they return to normal or until an etiology of the persistent abnormality is determined.

Globally, guidelines for blood collection volume limits for pediatric studies range between 1% and 5% of total blood volume (TBV) for a single draw (or during a 24-hour period) and up to 10% of TBV over 8 weeks [\(9\)](#). Scheduled collections in the current protocol, for the smallest possible patient (15 kg), remain within this limit for every 3 months. For all scheduled blood collection visits, the total volume does not exceed 1.5 mL/kg for the smallest possible patient.

Refer to [Section 17.7.2.2.2](#) for the description of the clinical laboratory evaluations and the schedule of laboratory evaluations performed throughout this study. The clinical laboratory parameters that will be measured in safety are:

Hematology:

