2.1.3 Efficacy endpoints

Efficacy endpoints are secondary endpoints of this study. The following efficacy endpoints will be analyzed:

- Annualized rate of severe asthma exacerbation events, during the treatment period.
- Change in percentage (%) predicted FEV1 and other lung function parameters (absolute FEV1, forced vital capacity [FVC, absolute and % predicted], forced expiratory flow [FEF] 25% to 75% [absolute and % predicted]) from baseline, and other time points assessed.

For spirometry parameters, the baseline values are the original baseline from the parent study.

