For change from baseline in pre-bronchodilator % predicted FEV1, absolute FEV1, FVC, and FEF 25%-75%, IE handling strategies are similar to the primary endpoint. Descriptive statistics (number of participants, mean, SD, median, minimum and maximum) and the 95% CI (based on t-distribution) of the mean will be presented over visits (Weeks 2, 4, 8, 24, 52, 64 for % predicted FEV1, and Weeks 2, 4, 8, 12, 24, 52, 64 for the others). In addition, figure of mean change from baseline (with corresponding standard error) will be presented for the parameter over visits.

Change from baseline in ACQ-IA

The global ACQ-7-IA score is the mean of the 7 questions of the Asthma Control Questionnaire—Interviewer Administered, 7-question version (ACQ-IA-7), and global ACQ-5-IA is the mean of the first 5 items.

For change from baseline in global ACQ-5-IA and ACQ-7-IA scores, IE handling strategies are similar to the primary endpoint. The methods for handling missing values of the questions are described in [Section 5.4](#). No missing data imputation will be performed for the global scores. Descriptive statistics (number of participants, mean, SD, median, minimum and maximum) and the 95% CI (based on t-distribution) of the mean will be presented over visits. Figure of mean change from baseline (with corresponding standard error) will be presented over visits.

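### In the Japan substudy, FVC and FEF 25-75% have no % predicted analysis, so their later changes mix normal growth with any drug effect

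*SAP*

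**What the plan says.** The Japan substudy SAP, section 1.2, has two lung-function items among its secondary endpoints. One is on the % predicted scale: "Change from baseline in pre-bronchodilator % predicted FEV1 at Weeks 2, 4, 8, 24, 52, and 64". The other is "Change from baseline in other lung function measurements (absolute FEV1, FVC, FEF 25-75%) at Weeks 2, 4, 8, 12, 24, 52, and 64". Protocol section 17.7.2.8.2 gives the same list.

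Section 3.3 of the Japan SAP keeps that split: "For change from baseline in pre-bronchodilator % predicted FEV1, absolute FEV1, FVC, and FEF 25%-75%, IE handling strategies are similar to the primary endpoint". For every parameter it plans descriptive statistics and a t-based 95% CI of the mean change at each visit, and adds "In addition, figure of mean change from baseline (with corresponding standard error) will be presented for the parameter over visits". No % predicted FVC or FEF 25-75% appears in the Japan SAP; the baseline spirometry list in Appendix 3 also names % predicted for FEV1 alone.

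The main-study SAP, section 2.1.3, specifies both scales: "forced vital capacity [FVC, absolute and % predicted], forced expiratory flow [FEF] 25% to 75% [absolute and % predicted". Section 2.1.3.2 repeats this. The main protocol endpoint (section 9.2.1) does not name % predicted for FVC or FEF 25-75% either, so the main SAP added it.

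On height in Japan, protocol section 17.7.2.8.3.2 says: "Height will be measured at each onsite visit except for the IMP administration only visit and Visit 9 (Week 36").

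**The concern.** The substudy is single-arm and open-label, and its children are followed for 64 weeks. The three dose regimens provide no untreated comparison. In a growing child, absolute FVC and FEF 25-75% are expected to rise even if lung function relative to body size does not change. A positive mean change at Week 52, with a confidence interval above zero, could therefore arise partly from growth.

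For FEV1 the reader can look across to % predicted at the same visit. For FVC and FEF 25-75% there is nothing to look across to. Week 64 has a further difficulty: it falls 12 weeks into the post-treatment period, and continued growth could hide some loss of effect on the absolute scale.

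What is at stake is how two named secondary efficacy parameters are read. Under Japan SAP section 3.7, the Week 52 results count as final in the study report.

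**Working it through.** **The plan's own figure.** The one precision statement is for % predicted FEV1 at Week 12: SD 14.12, n = 16, 95% half-width 7.5. Check: t(0.975, 15) × 14.12/√16 = 2.131 × 3.53 = 7.52. It reproduces and is not in dispute. There is no corresponding figure for FVC or FEF 25-75%.

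**Which scale is planned for each parameter**

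| Parameter | Main SAP 2.1.3 | Japan SAP 1.2 and 3.3 |
|---|---|---|
| FEV1 | absolute and % predicted | absolute and % predicted |
| FVC | absolute and % predicted | no % predicted; absolute on the natural reading |
| FEF 25-75% | absolute and % predicted | no % predicted; absolute on the natural reading |

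**Is % predicted derivable?** Protocol section 17.7.2.8.2.1 places post-screening spirometry at Weeks 0, 2, 4, 8, 12, 24, 52 and 64. The visit schedule in section 17.7.2.9.1 has height at each of those visits. Week 36, the exception for height, has no spirometry. No new assessment is needed. The main study measures height only at Visit 1 and EOT (protocol section 9.1.1), yet its SAP still plans % predicted.

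**How much could growth add?** None of these inputs is in the documents; all are assumptions:
- baseline height h₀: 115-145 cm
- growth g: 4-7 cm/year
- lung volume proportional to height to the power b, with b from 2 to 3

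Hold % predicted constant. The apparent rise in absolute volume at week w is then

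((h₀ + g × w/52) / h₀)^b − 1

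At Week 52:
- Low: (149/145)² − 1 = 5.6%
- Middle: (135.5/130)^2.5 − 1 = 10.9%
- High: (122/115)³ − 1 = 19.4%

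| Week | Low (145 cm, 4 cm/y, b = 2) | Middle (130 cm, 5.5 cm/y, b = 2.5) | High (115 cm, 7 cm/y, b = 3) |
|---|---|---|---|
| 12 | 1.3% | 2.5% | 4.3% |
| 24 | 2.6% | 5.0% | 8.7% |
| 52 | 5.6% | 10.9% | 19.4% |
| 64 | 6.9% | 13.5% | 24.2% |

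By construction, the same child shows zero change in % predicted. The scaling is for volume. FEF 25-75% is a flow and should move in the same direction, but these percentages should not be carried over to it.

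**The case against.** Several stronger readings are tempting, and the documents do not support them.

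- **That the SAP confines FVC and FEF 25-75% to absolute values.** It does not say so. The word absolute stands before FEV1, and the other two carry no scale of their own. The main protocol uses similar wording, and its SAP resolved it as both scales. Main SAP Appendix B also writes the two parameters without a scale. Absolute is the natural reading, but part of the problem is that the scale is left unstated.
- **That growth would be presented as efficacy.** Growth would be part of the observed change, not necessarily all of it. % predicted FEV1 is reported at every spirometry visit, so a growth-adjusted measure stands beside these results. The analyses are descriptive: multiplicity is marked not applicable, and no rule treats an interval excluding zero as benefit.
- **That Japan results cannot be set beside the main study's.** Absolute values are planned in both. The protocol analyses the two separately (section 17.7.2.10.4). The baselines differ too: parent-study baseline in the main study, last value before first dose in Japan. Adding % predicted would not make the changes comparable.
- **That % predicted must govern the efficacy reading.** Main SAP 2.1.3 gives both scales without ranking them for FVC or FEF 25-75%.

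Two further points count against a large claim. The Japan SAP follows the protocol's endpoint list, so it contains no deviation or contradiction. And % predicted would not isolate a drug effect: children enter with uncontrolled asthma, so regression to the mean remains on either scale.

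What survives is narrow. Two named parameters lack a growth-adjusted companion, and the data to supply one are already collected.

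**Conclusion.** The point holds in limited form. Followed as written, and on the natural reading of the scale, the Japan SAP will show FVC and FEF 25-75% changes that mix growth with any drug effect and cannot be separated from the planned tables. The effect is small at Weeks 2 to 12 and matters mainly at Weeks 24, 52 and 64. Under the stated assumptions, growth alone would account for about 6-19% of baseline lung volume at Week 52 and 7-24% at Week 64, against 1-4% at Week 12. The range is wide because every input is assumed.

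The primary endpoint, the sample size and the FEV1 conclusions are untouched. This is an inexpensive improvement to descriptive secondary endpoints in 13 enrolled children.

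**What to change.** In Japan SAP sections 1.2 and 3.3:

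1. State the scale on which FVC and FEF 25-75% are analysed.
2. Add change from baseline in % predicted FVC and % predicted FEF 25-75% at Weeks 2, 4, 8, 12, 24, 52 and 64. Use height at the visit and the same reference-equation source as % predicted FEV1, and name that source.
3. Keep the absolute values, with a footnote that they are not adjusted for growth.
4. Record the addition in section 3.8, since the protocol list does not contain it.

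The cost is two more derived parameters in tables and figures that already exist; no assessment is added and the sample size does not change. The growth-adjusted gains should look smaller than the absolute ones, so a late addition carries little risk of favouring the product.
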